6.0 Recruitment Methods

LOCAL:

- 6.1 This study will start with the retrospective phase which does not involve recruitment of patients, but involves analysis of existing data. De-identified data will be obtained from Cigna-Healthspring.
- 6.2 The project will be implemented in collaboration with Cigna-Health Spring, a Medicare Advantage Plan in Texas. The health plan has several electronic data files available for analysis including membership file, member

A motivational interviewing intervention customized by patient adherence patterns (NCT03985098) – 03.28.2018

summary file, institutional claims file, professional claims file, quest lab, Cigna-Health Spring's medical claims file (CCMS) and pharmacy file. Pharmacy files contain Part D pharmacy data provided by pharmacy benefits manager including patient/ drug identifying information, fill dates, days of supply, quantity dispensed and dosing for each prescription filled. The refill data will be used to determine the non-adherent patients. ICD-10 codes will be used to determine other exclusions using professional claims data.

Phase 2 will involve project intervention which will be conducted over the phone. A list of actively enrolled members, taking the medication who were a part of phase 1 will be created by Cigna HealthSpring to be used for intervention implementation at their premises. The phone call will be made by University of Houston pharmacy students who will be on rotation at Cigna-HealthSpring. The form of informed consent which will be read to the patient is attached to the IRB. If the patient consents to receive the intervention over the phone, and completes the phone call, the patient forms a part of the intervention group. Five follow-up phones will be attempted one month apart for the patient after the initial call.

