9.3 Phase 2: intervention implementation

Patients that are still enrolled in the health plan during 2017-2018 will be included in phase 2. Patients will be categorized by their adherence trajectory identified in phase 1 and will be randomized to intervention vs. not within each category. The proposed intervention will be a telephone call by a pharmacy student participating in rotations at Cigna-Health Spring Plan and trained in MI and 6 monthly follow up calls. During implementation, students will first examine the patient adherence pattern that was identified in phase 1 which will be coded. The student will then confirm the diagnosis, medication name, and dose with the patient answering the call and will follow the outlined protocol. Using MI, students will assess readiness for change, help patients identify potential barriers in accordance with patient past pattern of use, and guide them to develop a plan to deal with these barriers

A motivational interviewing intervention customized by patient adherence patterns (NCT03985098) – 03.28.2018

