15.0 Confidentiality

The intervention will occur on the premises of Cigna Healthspring. No identifiable data will leave the premises. Only encrypted, de-identified data will be available to [name] at UH. There will be no audio recording of the intervention. Only the research team operating from Cigna Healthspring will have access to identifiers.

The UH Pharmacy students who will conduct the intervention will only interact with the patients to conduct the intervention over the phone and will not be able to access any information on the patients otherwise. The students will collect notes about the phone calls to identify number of successful calls, number of attempts made to contact each patient, and barriers to adherence for the successful calls. These notes will be made in a single excel sheet which will be available only at Cigna – HealthSpring. The students will have no access to the notes otherwise. After the completion of the intervention phase, the excel sheet will be deidentified, and will contain a de-identified ID and corresponding barrier to adherence. This information will be provided to UH for understanding the success of the intervention process.

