To examine the effect of study group (intervention vs. control) on adherence, study group PDC means for each follow up time, 6 and 12 months, post intervention will be calculated and compared using a t-test. In the event that significant differences in baseline characteristics were observed, multiple regression will be utilized to adjust for the imbalance. The outcome variable will be PDC during each follow up period, 6 and 12 months, following the intervention initial call. The primary exposure variable will be study group, and other covariates will include any baseline characteristics not equally distributed.

Dichotomization of the outcome: Patients in both groups will also be categorized as adherent vs. not during the two follow up periods based on PDC \geq 80% in each time period, 6 and 12 months, to create 2 categorical outcome variables. The effect of study group on adherence will be evaluated for these categorical outcomes using chi-square tests. If significant differences in baseline characteristics were observed, logistic regression models will be utilized to adjust for imbalances

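### If adherence varies with the student who makes the calls, the planned tests understate the uncertainty, and student identity is not among the data listed for collection or transfer

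*Combined protocol and SAP*

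**What the plan says.** Section 9.3 randomises individual patients: within each trajectory category they "will be randomized to intervention vs. not within each category". The same section describes delivery: "The proposed intervention will be a telephone call by a pharmacy student participating in rotations at Cigna-Health Spring Plan and trained in MI". Section 6.0 agrees: "The phone call will be made by University of Houston pharmacy students who will be on rotation at Cigna-HealthSpring". Controls receive no call.

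Under Outcome analysis in section 20.0, mean PDC at 6 and 12 months is compared with a t-test ("post intervention will be calculated and compared using a t-test"). For PDC dichotomised at 80%, "The effect of study group on adherence will be evaluated for these categorical outcomes using chi-square tests". If baseline is imbalanced, multiple or logistic regression is used, and "other covariates will include any baseline characteristics not equally distributed". No section mentions clustering by student, an ICC, a design effect, a random effect or a robust variance.

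On data, section 15.0 states: "The students will collect notes about the phone calls to identify number of successful calls, number of attempts made to contact each patient", together with the barriers found. The sheet sent to the university is described as holding a coded patient ID and the matching barrier. Section 9.3 adds the date and a summary of the first call. None of these lists names the student.

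The plan does not state the number of students, how patients are assigned to them, whether one student makes all six calls to a patient, or the significance level.

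**The concern.** Motivational interviewing depends on the skill of the person who does it. Patients called by the same student share that student's ability, so their later refill behaviour may be correlated. Controls have no student, so any such correlation sits in one arm only. This is a partially nested design. A two-sample t-test or chi-square test leaves the between-student variance out of the standard error of the difference.

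The third objective in section 8.0 is to demonstrate benefit, and section 2.0 looks ahead to wider use of tailored interventions. If a few able students drive the result, the planned analysis would present it as a property of the programme, with an interval that is too narrow for that claim. Without the student's identity in the analysis data, the analysts could not check this.

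**Working it through.** **The plan's own figure.** Section 5.2 gives 250-300 intervention patients with one control each: 2 × 250 = 500 and 2 × 300 = 600, which matches the stated total. No power-based check is possible, because significance level, power, effect size and standard deviation are not given.

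**Inputs**
- n = 250-300 per arm (section 5.2).
- K = 8-20 students: assumed.
- ICC = 0.01-0.05: assumed.
- Nominal two-sided 5% test: assumed.
- Each called patient belongs to one student, clusters are of equal size, and total variance is equal in the two arms: assumed.

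**Formulas**
- Patients per student: m = n/K.
- Design effect in the intervention arm: DE = 1 + (m − 1) × ICC.
- True over naive variance of the difference: R = (1 + DE)/2, because the control arm is not clustered.
- Actual error when the mean effect is zero but students differ: 2 × [1 − Φ(1.96/√R)].

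**Results**

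| n per arm | K | ICC | m | DE | R | √R | Actual error |
|---|---|---|---|---|---|---|---|
| 250 | 10 | 0 | 25.0 | 1.000 | 1.000 | 1.000 | 5.0% |
| 250 | 30 | 0.01 | 8.3 | 1.073 | 1.037 | 1.018 | 5.4% |
| 300 | 30 | 0.01 | 10.0 | 1.090 | 1.045 | 1.022 | 5.5% |
| 250 | 20 | 0.01 | 12.5 | 1.115 | 1.058 | 1.028 | 5.7% |
| 250 | 12 | 0.02 | 20.8 | 1.397 | 1.198 | 1.095 | 7.3% |
| 300 | 12 | 0.02 | 25.0 | 1.480 | 1.240 | 1.114 | 7.8% |
| 300 | 8 | 0.05 | 37.5 | 2.825 | 1.913 | 1.383 | 15.6% |

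The column √R is the factor by which the naive standard error should be multiplied. In the middle case (12 students, ICC 0.02) the interval should be about 9%-11% wider.

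**Simulation check** of the pooled t-test, 20,000 runs per setting:
- n = 250, K = 10, ICC 0: 4.97% (formula 5.0%)
- n = 250, K = 10, ICC 0.01: 6.2% (6.4%)
- n = 250, K = 10, ICC 0.05: 12.2% (12.1%)
- n = 250, K = 20, ICC 0.01: 5.7% (5.7%)
- n = 300, K = 20, ICC 0.05: 9.2% (9.2%)

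**If uncalled patients are analysed.** Section 20.0 promises intent to treat. Suppose half of the arm is called. Then m = (n/2)/K, the arm's variance factor is (DE + 1)/2, and R = [1 + (DE + 1)/2]/2.
- n = 250, K = 20, ICC 0.01: m = 6.25, DE = 1.053, R = 1.013, error about 5.2%.
- n = 300, K = 8, ICC 0.05: m = 18.75, DE = 1.888, R = 1.222, error 7.6%.

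**The case against.** The case on the other side has real force, and most of it limits how strongly the point can be put.

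- **A certain excess over 5%.** A reader might infer that the error rate does exceed 5%. The documents do not support that. Patients are individually randomised, so if the calls change nobody's behaviour, students create no correlation and the t-test keeps its level. The excess needs a zero mean effect with real differences between students. Separately, the interval is too narrow whenever students differ and the result is generalised beyond them.
- **A small pool of students.** This too might be inferred, but no number is given. Rotations over 8 months of enrolment (section 7.4) make turnover plausible, and with many students the effect is slight.
- **One student per patient.** Six calls are planned, and nothing says one student makes them all. Several callers would dilute the clustering and make simple nesting by the first caller an approximation.
- **Every intervention patient is called.** Section 6.0 suggests so: a patient who consents "and completes the phone call, the patient forms a part of the intervention group". Section 20.0 promises intent to treat. Analysis as randomised would bring in patients with no student and weaken the effect.
- **Standardisation.** Students share three days of training, written protocols and supervision, and PDC comes from refill records, not from the students. This argues for a low ICC. It does not show that the ICC is zero.
- **Students as fixed.** If the conclusion is confined to the participating students, the student variance need not enter the standard error. That choice is legitimate, but it sits badly with the wider use described in section 2.0, and the plan does not make it.
- **A student effect that can never be modelled.** This is too strong. The call sheet stays at the health plan, and first-call dates are recorded, so the caller might be recovered. The documents show only that identity is not listed.

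**Conclusion.** The point holds in conditional form. What the documents establish is that students deliver the calls in one arm, that no planned analysis allows for it, and that student identity is not among the listed data. If outcomes vary by student, the planned tests understate the uncertainty about the programme.

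The size rests on assumptions. The range of 5.7%-15.6% is for 8-20 students, ICC 0.01-0.05, 250-300 called patients per arm and full nesting. Its upper end is the least favourable corner of that grid. With half the arm uncalled, the same grid gives about 5.2%-7.6%. The concern therefore runs from negligible to material, and only the number of students and the observed ICC can settle which. The change is worth making because it is cheap and the student ID is best captured while the calls are under way.

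**What to change.** 1. **Sections 9.3 and 15.0:** add a coded student ID for every call, first and follow-up, to the call sheet, and include it in the de-identified transfer.
2. **Section 20.0, PDC:** prespecify a partially nested mixed model in place of the t-test. Give it a random student effect in the intervention arm only, clustering by the student who made the initial call, arm-specific residual variances and small-sample degrees of freedom (Kenward-Roger in SAS PROC MIXED). Treat controls and uncalled patients as clusters of one.
3. **Section 20.0, PDC of at least 80%:** use the matching mixed logistic model in place of the chi-square test.
4. **Several callers:** add a sensitivity check for patients called by more than one student, since clustering by the initial caller is then an approximation.
5. **Reporting:** give the number of students and the estimated ICC with the result.

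The cost is one column in the call sheet and a few lines in SAS, which the plan already names. The interval may become somewhat wider, with fewer degrees of freedom if there are few students. If the student variance is estimated at zero, the result is essentially the one now planned.

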9.0 Procedures Involved

9.1 Phase 1: Retrospective data analysis

Patients that used a study medication during January 2017 will be identified and the first prescription date during this time will be considered the index date. A dummy variable will be created to indicate prevalent user vs incident user by evaluating the 6 month data prior to index date (July – December 2016). Patient adherence will be assessed during the one year following the index date.

Adherence will be measured as proportion of days covered (PDC). PDC rates over the entire 360-day assessment period will be determined. PDC will also be calculated separately for each month during the one year following the index date. During each of the 12 consecutive 30-day periods of adherence assessment, a binary indicator for “full adherence” each month, defined as PDC= 0.8 vs. non-adherence will be created. The 12 binary indicators of full adherence will then be modeled during each 30-day period as a longitudinal response in a logistic group-based trajectory model. Patients will be assigned to a trajectory on the basis of these models. Several logistic regression models will then be carried out to identify predictors associated with specific trajectories for adherence.

9.2 Covariates: Demographics (age, gender, and language), physician specialty (primary care vs. specialist), health plan (low income subsidy vs.

A motivational interviewing intervention customized by patient adherence patterns (NCT03985098) – 03.28.2018

other), prevalent vs. incident user, Centers for Medicare and Medicaid CMS Risk Score, Charlson comorbidity index (CCI) and number of distinct medications. Additionally, selected co morbidities will be identified by ICD-10 codes during the one year prior to index date including congestive heart failure, coronary artery disease, peripheral vascular disease, myocardial infarction, diabetes, stroke hypertension, end stage renal disease (ESRD), chronic obstructive pulmonary disease, asthma, and depression. To ensure appropriate risk adjustment in the models, additional covariates which will be added to the model include, regimen complexity, class of antihypertension medication used, baseline adherence measured as PDC, previous hospitalization and patient's trajectory prior to intervention.

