20.0 Data Management

- 20.1 The data which will be provided by Cigna will contain data with encrypted patient IDs. The electronic data files for this study will be processed on a dedicated, layered-security server, which can be accessed only by [name] and designated project staff members who are under the direct supervision of [name]. Since the system is behind multiple firewalls, is monitored regularly, and is accessible only to key personnel, the risk of unlawful penetration is not a significant data safeguard concern. Data will be stored on the secure server for 3 years following the completion of the study. All analysis will be conducted on the desktop at UH College of Pharmacy. The data will not be accessible through any personal computers.

SAS 9.4 is the statistical software, which will be used for the analysis.

A motivational interviewing intervention customized by patient adherence patterns (NCT03985098) – 03.28.2018

Baseline characteristics: Comparisons in baseline characteristics will be made between the 2 study groups (intervention vs. control) using t-tests for continuous variables and chi-square tests for categorical variables. The characteristics evaluated will include predisposing factors: demographics, and number of other medications used; enabling factors: health plan (LIS vs. not), prescriber specialty (specialist vs. primary care); need factors: comorbidities (CHF, MI, CAD, stroke, ESRD, depression), previous hospitalization and CMS risk score.

Baseline PDC in the 12 months prior to intervention and patient past adherence trajectory will also be compared between 2 groups. Because of the randomization, we do not anticipate any significant differences between the two study groups on these characteristics.

Outcome analysis: Refill data during 2 time periods -- 6, and 12 months, following the initial call of the intervention will be evaluated to calculate adherence rates for both the intervention and control groups. The two periods were chosen to evaluate the intervention effect during the 6 months when the follow up calls were ongoing as well as after these calls had stopped. The adherence rate will be defined as proportion of days covered (PDC) for six and twelve month follow up period following the intervention. An intent to treat analysis will be utilized.

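### Section 20.0 makes adjustment for baseline PDC and trajectory stratum conditional on baseline significance tests, section 9.2 appears to plan it unconditionally, and neither the unadjusted nor the adjusted result is given precedence

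*Combined protocol and SAP*

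**What the plan says.** **Outcome analysis (section 20.0).** Mean PDC is compared between groups by t-test at 6 and at 12 months. Regression is conditional: "In the event that significant differences in baseline characteristics were observed, multiple regression will be utilized to adjust for the imbalance". On its content, the section says that "other covariates will include any baseline characteristics not equally distributed".

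**Dichotomised outcome (section 20.0).** For PDC of at least 80%, "The effect of study group on adherence will be evaluated for these categorical outcomes using chi-square tests". The same condition follows: "If significant differences in baseline characteristics were observed, logistic regression models will be utilized to adjust for imbalances".

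**What is tested at baseline (section 20.0).** After the demographic, plan, prescriber and comorbidity variables, the section adds: "Baseline PDC in the 12 months prior to intervention and patient past adherence trajectory will also be compared between 2 groups".

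**Randomisation (section 9.3).** Patients are grouped by Phase 1 trajectory and "will be randomized to intervention vs. not within each category". Trajectory is therefore the stratification factor.

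**Covariate list (section 9.2).** "To ensure appropriate risk adjustment in the models, additional covariates which will be added to the model include, regimen complexity". The same sentence goes on to name baseline PDC and the patient's trajectory before the intervention. It sets no significance condition and does not say which model is meant.

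**Precedence.** Section 8.0 (endpoints), section 9 and section 20.0 do not say whether the unadjusted or the adjusted comparison is the main one.

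**The concern.** Under section 20.0 two covariates that are likely to predict follow-up PDC are adjusted for only if a baseline test happens to be significant. In a randomised comparison such a test reflects chance. It is a poor guide to which covariates matter, because the value of a covariate depends on how strongly it predicts the outcome. The stratification factor is subject to the same trigger. If the strata are balanced by design, its test will hardly ever be significant, and the unadjusted t-test then overstates the standard error.

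Three things are at stake:

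- precision that the trial could have from data it already plans to hold;
- a clear reading of sections 9.2 and 20.0, which point in different directions;
- the choice of result. When a baseline test is significant, two results exist, and the choice between them stays open after the data are seen.

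**Working it through.** The plan gives no power calculation, alpha, effect size or SD, so there is no stated figure to reproduce. The only sample-size arithmetic, 2 × 250 = 500 and 2 × 300 = 600 (section 5.2), is correct.

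**Inputs.** From the documents: 250 per group (lower end of section 5.2) and the list of tested characteristics (section 20.0). Assumed: two-sided alpha 0.05, PDC difference 0.06, SD 0.30, and correlation r between baseline and follow-up PDC of 0.2 to 0.6. A low r is plausible because Phase 2 takes only non-adherent patients (section 2.1), which narrows the baseline range.

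**Step 1: how often the trigger fires by chance.** Counting age, gender and language (the demographics named in section 9.2), medication count, low-income subsidy, prescriber specialty, six comorbidities, hospitalisation and CMS risk score gives 3 + 1 + 1 + 1 + 6 + 1 + 1 = 14 tests. Baseline PDC and trajectory make 16. If the tests are independent:

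- 1 − 0.95^14 = 0.512
- 1 − 0.95^16 = 0.560

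With all tests correlated at 0.3, simulation gives 44% and 48%.

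**Step 2: power, unadjusted and with pre-specified adjustment.** Expected z = 0.06 / (0.30 × √(1 − r²) × √(2/250)). Unadjusted (r = 0), this is 0.06 / 0.02683 = 2.236, so power is 0.609. At r = 0.6 it is 2.236 / 0.8 = 2.795, so power is 0.798.

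**Step 3: the rule as written.** The wording on covariates allows two readings:

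- *First reading:* baseline PDC enters only if its own test is significant.
- *Second reading:* any significant baseline test brings in a model that contains baseline PDC.

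Both were simulated from the joint distribution of the baseline and follow-up z-statistics, with simple randomisation and 14 other independent tests.

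| r | Unadjusted | Rule, first reading | Rule, second reading | Pre-specified |
|---|---|---|---|---|
| 0.2 | 0.609 | 0.610 | 0.618 | 0.626 |
| 0.3 | 0.609 | 0.612 | 0.631 | 0.650 |
| 0.4 | 0.609 | 0.614 | 0.650 | 0.684 |
| 0.6 | 0.609 | 0.622 | 0.712 | 0.798 |

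**Step 4: sensitivity to the SD.** At SD 0.25 and 0.35, unadjusted power is 0.765 and 0.483. With adjustment it is 0.782 and 0.499 at r = 0.2, and 0.918 and 0.669 at r = 0.6.

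**Step 5: type I error.** Under the rule it is 0.049 falling to 0.040 as r rises from 0.2 to 0.6 (first reading), or 0.050 falling to 0.045 (second). If whichever result is significant were claimed, it would be 0.051 (first) or 0.055 to 0.065 (second). With exact stratum balance, the unadjusted t-test has type I error 2 × (1 − Φ(1.96 / √(1 − R²))). This is 0.039 if strata explain 10% of outcome variance and 0.024 if they explain 25%, so the test is conservative.

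**Step 6: how often two results exist and disagree.** At the assumed effect, both results exist and differ on significance in about 1-2% of trials (first reading) or 4-13% (second).

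**Step 7: sections 9.2 and 20.0 side by side.** Section 20.0 allows baseline PDC and trajectory into the outcome model on a trigger; section 9.2 adds them without one. Section 9.2 follows the Phase 1 methods, but trajectory is itself the outcome of the Phase 1 predictor models. A covariate described as trajectory before the intervention therefore fits the Phase 2 outcome model better. This is an inference, since the text does not name the model.

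**The case against.** The strongest reply is that section 9.2 already plans the adjustment. If its list governs the Phase 2 outcome model, baseline PDC and trajectory are in that model whatever the baseline tests show, and only a drafting conflict remains. This stands in part: it is why the conflict is probable rather than proven. It does not settle the matter, because section 20.0 is the more specific text on the outcome analysis and states the trigger twice.

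A second reply is that the harm is small. This also stands. At r of 0.2 to 0.3, pre-specified adjustment gains 2 to 4 points of power over the unadjusted test, and the assumed SD moves power by more than that.

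A reader might infer three stronger things that the documents do not support:

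- *That conditional adjustment biases the estimate.* Under randomisation, chance imbalance is already in the t-test's standard error; it is imprecision. Selection through consent and call completion (section 6.2) is a different problem, which these covariates would not cure.
- *That the rule inflates type I error.* In the scenarios examined it stays at or below 5%. Only picking the significant result goes above that, to 6.5% at most.
- *That the two results will often conflict.* An adjusted result exists only after a trigger. Comparing the unadjusted test with an always-adjusted one across all trials gives 6-24% disagreement, but that is not what the plan would produce.

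Finally, the choice of a primary time point is a separate multiplicity question. The section gives a reason for having both periods, namely to "evaluate the intervention effect during the 6 months when the follow up calls were ongoing as well as after these calls had stopped", and the covariate point holds for each.

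**Conclusion.** The point holds as one of precision and pre-specification. Section 20.0 leaves adjustment for baseline PDC and the randomisation stratum to chance test results, section 9.2 probably says otherwise, and nothing ranks the two results.

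With 250 per group and the assumed difference, SD, alpha and correlations, the rule forgoes most of the available power gain on the first reading and about half of it on the second. The loss is minor if r is low and material if r is near 0.6: 62% or 71% against 80%. By chance alone the trigger has roughly even odds of firing, so a trial with two results and no stated precedence is a realistic prospect, although they would differ on significance in only a minority of trials.

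Confidence is high that precedence is unstated, and lower that section 9.2 contradicts section 20.0. The power figures rest on values that the documents do not give. The change should be made, but nothing here would invalidate the trial.

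**What to change.** Before any Phase 2 outcome data are seen, replace both conditional sentences in section 20.0 with text such as:

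> The primary analysis of PDC at each follow-up period is a linear regression on study group, baseline 12-month PDC and trajectory stratum. PDC of at least 80% is analysed by logistic regression with the same terms, and its odds ratio is conditional on them. Baseline comparisons are descriptive and do not decide the covariates. The t-test and chi-square test are sensitivity analyses.

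In section 9.2, name the model to which the covariate list belongs and align the list with section 20.0.

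Define baseline PDC from an index date that exists for every patient in the intent-to-treat set promised in section 20.0, for example the randomisation date. The initial-call date does not serve: patients randomised to intervention but never reached have none, and neither do controls. Borrowing the date of a called patient would cover only the controls drawn under section 9.3.

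The cost is minor wording and analysis work. Refill data and trajectory are already planned, so no new data are needed. The report must state that the odds ratio is conditional.
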